9.3 Definition of Populations

For this study, the per-protocol population will include all participants who completed all assessments and interventions with no major protocol deviations (as defined by Gupta, 2011). The primary analysis will be conducted on the Intent-to-Treat (ITT) population that will include all randomized participants who have completed baseline assessments. In the original trial, all FORT completers participated in all assessments, but approximately 20% of Treatment as Usual participants were lost to follow-up. Analysis of baseline data revealed that most missing data were missing at random.

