6.2 Description of Evaluations

6.2.1 Enrollment and Screening Evaluation (Week -4 to Week 0; See Figure 3)

All screening will occur within 4 weeks after consent (so consent occurs at Week -4)

Consenting Procedure

Potential participants will have the study explained to them in a safe and private location. The Veteran will be given a copy of the informed consent document (ICD) to read. The research team member obtaining informed consent will then engage the Veteran in an interactive explanation of the study guided by the Informed Consent Form. After the Veteran has read the ICD, they will be given the opportunity to consider participation and discuss the research with other family and friends. The Research Team will be available to answer any questions about the research. Once the potential participant has reached a decision, the advising staff member will review the risks and benefits of study participation and ensure the Veteran has an understanding of the material discussed, and the risks and benefits of their potential involvement in the study. The advising staff member will have the participant sign the consent form. A copy of the signed ICD will be given to the Veteran. STRONG STAR addresses issues related to mental capacity of potential participants through ongoing screening procedures using trained independent evaluators. Any concern that a potential participant is unable to comprehend what is being asked of them to participate in the research or the consent document will be referred to a licensed psychologist for additional assessment. Similarly, any concerns identified during the course of the study that participants may no longer comprehend what is being asked of them or be able to engage in the study procedures will be referred to a licensed psychologist and the research team. All Veterans who have provided informed consent will be considered enrolled to the study. Consent will be tracked for each participant using the NCCIH Screening and Enrollment Log (**Appendix A3**).

Screening

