Depressive Symptom Inventory-Suicidality Subscale (No active suicidal ideation or intent)		Veterans cannot enroll if they report suicidal ideation with intent. There is no widely accepted cutoff score for this on the BSSI, so any

		positive BSSI score will need to be reviewed by the PI and Psychologist Co-Investigators and the PI will make a decision on inclusion
Ohio State University TBI Scale Short Form – VA		Veterans cannot participate with severe TBI-related cognitive impairment
(No severe TBI-related cognitive difficulty)		
MINI (Psychosis Module)		Screen out psychosis
Pregnancy Test		Screen for pregnancy

The outcome of all screening will be briefed to the PI and Co-Investigators during a weekly study meeting (in a de-identified format) for a final determination of each enrolled participant’s eligibility for the study. Once confirmed eligible, participants are randomized. The PI will adjudicate any unclear determinations of eligibility for enrollment and the determination will be entered into the enrollment log.

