6.2.2 Randomization and Baseline

Randomization (Wk -4 to 0)

Once the PI and Co-Investigators have determined that a participant has satisfactorily met all inclusion/exclusion criteria, the participant will be randomized by the study coordinator (this could be done at any time from week -4 to week 0 as long as consenting and screening come first). The date of randomization will be recorded on the Enrollment Log.

The maximum allowable time between enrollment and randomization is 4 weeks. If screening and determination of eligibility goes beyond this allowable window, the participant will need to be re-screened before randomization.

Baseline Assessments (Week 0; See Figure 4)

Baseline assessment occurs within 4 weeks from the time of enrollment (regardless of when baseline assessment occurs relative to screening, Baseline Assessment is identified as Week 0).

For participants who have successfully been screened for eligibility and are randomized into the study, baseline assessments are performed to measure the study outcomes. They also ensure that the groups are balanced with respect to baseline characteristics.

Baseline evaluations for this study include:

Assessments (Domain Assessed)	Assessment Window	Special Instructions
----------------------------------	----------------------	----------------------

Health Questionnaire / Addendum (previous pain treatments) (comorbid pain/medical conditions)	≤ 2 weeks before treatment start	Balance Sample Past medical history will not change, so this measure is only given once
Concomitant Medications and Medication Quantification Scale- III (medications that may impact pain) (medications that may impact mood)		Control: Other Medications Medications may change, so this will be assessed at all assessment visits; self-report and CPRS review
Timeline Follow-back Interview (opioid & other pain medication use)		Endpoint: Hypothesis 3 Assessed at all assessment visits
Oswestry Disability Index (self-report disability)		Endpoint: Hypothesis 1 Veterans cannot participate with moderate to severe TBI- related cognitive impairment
PHQ-9 (depression symptoms)		Endpoint: Hypothesis 2 Assessed at all assessment intervals
PTSD Checklist – 5 (PTSD symptoms)		Endpoint: Hypothesis 2 Assessed at all assessment intervals

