9. STATISTICAL CONSIDERATIONS

9.1 General Design Issues

Primary Hypothesis: FORT-A participants will demonstrate significantly greater improvements in self-reported than those receiving PRC treatment as usual (TAU).

“Greater improvement” is defined in this study as statistically significant **lower** ODI scores for FORT-A compared to TAU at one-year post-treatment follow-up controlling for differences in ODI at pre-treatment. Logic for selection of ODI as the primary outcome is described in Section 3 of this protocol. Validity and reliability of the ODI has been well-established in over 100 published studies, and use of the ODI will allow comparison of the proposed study results to numerous other pain populations and interventions (allowing for better prediction of result generalizability outside of the population of interest; Fairbank et al., 1980; Fairbank & Pynsent, 2000).

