9.6 Data Analyses

Data Analysis: To examine our aims and hypotheses we will utilize the generalized linear model, which allows specification of an appropriate distribution for each outcome that can accommodate continuous outcomes (e.g., normal distribution with identity or log link for self-reported disability) and presence/absence outcomes (e.g., binomial with logit link for probability of daily opioid use). We will not stratify our analyses by PTSD or depression, but will account for these variables in our data analysis. Furthermore, we will attend to the influence of missing data on our analyses, and plan on conducting missing values analysis to inform several sensitivity analyses (e.g., LOCF, multiple imputation, etc.) to ensure an intent-to treat principle is observed. Specifically, we will examine the MAR assumption by examining patterns of missingness conditional on baseline assessments, treatment adherence, or other time-varying predictors. Our RCT has one primary endpoint (Oswestry), so both primary and secondary outcomes will be interpreted at a conventional level of statistical significance, $p < 0.05$. To adhere to NIH policy of examining gender and ethnic subgroup analyses, we will add interaction terms (i.e., treatment group x subgroup) for each of our planned analyses. Each analysis is further detailed below:

AIM 1: Assess the efficacy of the FORT-A Program for improved pain management outcomes in (N=130) polymorbid OEF/OIF/OND PRC Veterans with chronic orthopedic pain using a 1:1 randomized clinical trial comparing FORT-A to standard PRC care. To examine our primary hypothesis, we will compare the self-reported disability scores of the two groups at 12-month follow-up while controlling for baseline scores (i.e., an ANCOVA approach). A statistically significant main effect will be interpreted as the groups exhibiting differential change in regards disability. Secondary analyses will use growth curve modeling (mixed effects hierarchical regression with polynomial change parameters) which will model differences in change trajectory over time between the groups across assessment occasions.

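### The primary analysis set called intent-to-treat leaves out randomised participants who did not complete baseline, although baseline follows randomisation; it is a modified ITT set

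*Combined protocol and SAP*

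**What the plan says.** **Analysis set.** Section 9.3: "The primary analysis will be conducted on the Intent-to-Treat (ITT) population that will include all randomized participants who have completed baseline assessments".

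**Order of events.** Section 6.2.1, after the screening results are reviewed: "Once confirmed eligible, participants are randomized". Section 6.2.2: "For participants who have successfully been screened for eligibility and are randomized into the study, baseline assessments are performed to measure the study outcomes". The same section allows randomisation at any time from week -4 to week 0, provided that consent and screening come first. The schedule in section 6.1 heads the randomisation column as up to 4 weeks before baseline.

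**Length of the gap.** Section 6.2.2: "Baseline assessment occurs within 4 weeks from the time of enrollment". Enrolment means consent (section 6.2.1): "All Veterans who have provided informed consent will be considered enrolled to the study". The interval from randomisation to baseline is therefore bounded at about four weeks and can be close to nothing.

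**Primary model.** Section 9.6, Aim 1: "we will compare the self-reported disability scores of the two groups at 12-month follow-up while controlling for baseline scores". Section 9.1 describes the same adjustment: "controlling for differences in ODI at pre-treatment".

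**Missing data.** Section 9.6 plans a missing-values analysis and sensitivity analyses such as LOCF and multiple imputation, "to ensure an intent-to treat principle is observed". Section 9.2 expects up to 30% of participants to need some imputation.

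**Masking.** Section 9.2 (Treatment Assignment Procedures) says that participants and providers cannot be masked.

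**The concern.** An intent-to-treat set keeps the groups as randomised. Here a participant must also have completed baseline, which is done after the arm has been allocated. One arm asks for 4½ hours a day on 12 days over three weeks (section 5.1) and the other is usual care, so early loss could differ by arm. If it did, and those lost had a different prognosis, the primary contrast would no longer be protected by randomisation.

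Section 9.3 also does not say which assessments must be complete. The extracted schedule in section 6.1 marks 25 items with an X in the baseline column, and the example log in section 5.4 tracks five assessment domains separately. A wide reading would exclude more people than a reading confined to the ODI.

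**Working it through.** **1. The sequence.** Consent (enrolment) → screening, including an ODI → eligibility confirmed → randomisation → baseline assessments, including a second ODI → treatment. Section 9.3 conditions on the fifth step, after allocation at the fourth. Nothing in the text requires baseline to be completed before randomisation, and nothing returns a person whom section 9.3 has left out.

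**2. The plan's own power figure.** Section 9.2 gives 65 per arm, SD 6.6, a difference of 3.3 (d = 3.3/6.6 = 0.50), two-sided alpha 0.05 and power 0.80. Unadjusted, Φ(0.50 × √(65/2) − 1.96) = Φ(0.890) = 0.813, so the figure reproduces. The point about the analysis set does not depend on it.

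**3. Size of a possible shift.** The documents give no pre-baseline loss rate. Assumed inputs are loss differing between arms by 5 to 10 percentage points, and those lost scoring 3 to 5 ODI points worse at 12 months than those retained, with none of that gap explained by baseline ODI.

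Shift = (difference in loss) × (gap):

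| Difference in loss | Gap (points) | Shift (points) | Share of 3.3 |
|---|---|---|---|
| 0.05 | 3 | 0.15 | 4.5% |
| 0.05 | 5 | 0.25 | 7.6% |
| 0.10 | 3 | 0.30 | 9.1% |
| 0.10 | 5 | 0.50 | 15.2% |

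A higher ODI is worse, so the shift favours the arm that loses more. In people, the difference is 0.05 × 65 = 3.25 to 0.10 × 65 = 6.5 in one arm. Simulated ANCOVAs with 65 per arm agree: a shift of 0.16 for 10% against 5% loss with a gap of 3, and 0.50 for 15% against 5% with a gap of 5.

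**4. What that would do to the test.** Take an assumed baseline to 12-month correlation of 0.5 and 2n − 3 degrees of freedom. SE = 6.6 × √(1 − 0.25) × √(2/n). The false-win column is the one-sided chance of a false FORT-A win.

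| n per arm | SE | Power for 3.3, no shift | Power, shift of 0.15 to 0.5 against FORT-A | False win, no shift | False win, shift of 0.15 to 0.5 for FORT-A |
|---|---|---|---|---|---|
| 65 | 1.003 | 0.904 | 0.877 to 0.791 | 0.025 | 0.035 to 0.071 |
| 45 (65 × 0.7 = 45.5) | 1.205 | 0.773 | 0.734 to 0.632 | 0.025 | 0.033 to 0.061 |

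**5. When the shift is zero.** (a) Nobody is lost before baseline. (b) Loss is equal in the two arms with the same outcome gap. (c) Loss differs between arms but depends only on baseline ODI, which the ANCOVA adjusts for. Case (c) was simulated with 65 per arm, correlation 0.5 and loss of 15% against 5%. Those lost scored 2.2 points worse at 12 months, yet leaving them out moved the adjusted contrast by only −0.01. The figures in steps 3 and 4 therefore apply only to the part of the gap that baseline does not explain.

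**The case against.** **No loss is shown.** Nothing in the documents shows that anyone leaves between randomisation and baseline, and the gap can be very short. This stands. The defect in the definition is certain; harm from it is not.

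**Section 9.6 protects the principle.** It protects it only for people already in the set. The intent-to-treat phrase there closes a sentence on missing-data sensitivity analyses and does not redefine the population.

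**ANCOVA needs a baseline value.** It does, but an ODI is an entry criterion (section 4.1), is collected at screening (section 6.2.1) and is confirmed as a screening measure in section 9.5.1. Every participant randomised under the protocol should therefore have a pre-randomisation ODI.

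**Stronger readings that a reader might infer, and that the documents do not support:**

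- *A badly inflated type I error.* A rate near 19% can be computed, but it needs 20% loss in one arm only and a gap of a full SD. Neither input is in the documents.
- *People dropped for a missing functional test.* The primary model needs only the ODI. The wording is ambiguous, which is a reason to define it and not evidence that anyone would be dropped on this ground.
- *A baseline ODI distorted because participants already know their arm.* The text reviewed does not settle when they are told. Figures 3 and 4, which cover this sequence, are not shown, so silence cannot be inferred.
- *Differing statements on coordinator blinding.* These do not bear on who is in the analysis set.

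**Conclusion.** The concern holds as a defect of definition. The primary population is a modified ITT carrying the ITT label, it rests on a condition met after allocation, and that condition is not fully specified. This is clear from the text and needs no assumption.

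The numerical consequence is unknown and may be zero. On the assumed inputs above it is at most about 0.5 ODI points (15% of 3.3), and only for loss that differs by arm and is not explained by baseline ODI. It should be fixed because the correction is cheap and removes a post-allocation exclusion from an unmasked comparison. It does not show that the trial's result would be wrong.

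**What to change.** In section 9.3, before data lock and while the biostatistician is still blind (section 3), write:

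> The ITT population includes all randomised participants, analysed in their assigned arm, whether or not baseline was completed. Where the baseline ODI is missing, the pre-randomisation screening ODI is used as the covariate. Losses between randomisation and baseline are reported by arm.

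Keep the present set as a sensitivity analysis, labelled modified ITT and defined by a completed baseline ODI.

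**Cost.** N stays at 130, and the covariate is unchanged for everyone with a baseline ODI. If nobody is lost before baseline, the ITT set is simply all 130. If 5 to 10% are lost (assumed), 130 × 0.05 = 6.5 to 130 × 0.10 = 13, so about 7 to 13 more people need follow-up or imputation.

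**Downside.** Section 6.2.5 seeks final assessments from everyone and an ODI from those lost to contact. The latter is a telephone contact after a letter with an opt-out, and it was added only in version 10.0 (September 2019) of a trial planned for 2014 to 2019. The 12-month ODI of people lost early may therefore have to be imputed largely from the screening ODI, and the report should say so.

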9.4 Interim Analyses and Stopping Rules

Interim analyses will not be completed as part of this research. We were fortunate to have solid data from the original FORT trial to help estimate power for the proposed research, and the resulting power analyses are solid. Thus, we do not anticipate uncovering changes in the primary outcome that would necessitate a need for early stoppage or futility of the proposed research and do not feel that we have any preliminary impetus for spending alpha in pursuit of these interim analyses. In conclusion, we do not anticipate observing evidence for early futility or superiority in this trial until all data are gathered in accordance with our in-place power analysis.

The interventions used in this study have been thoroughly studied in other research and it is predicted that the need for a safety review will be low. However, there are some circumstances that would require suspension of study activity and review of safety by an ad hoc safety review committee as follows:

- This is one of the first studies of an interdisciplinary pain program for chronic pain and trauma polymorbidity. The PIs STRONG STAR Pain and PTSD Study revealed no significant exacerbation of PTSD symptoms in a combined pain and PTSD protocol, but PT was not involved in that protocol. There is no reason right now to believe that Physical Therapy will exacerbate PTSD symptoms, but if this were to occur (based on a 20 point increase on the PCL-5) then a safety review would be needed to determine if the study must stop. This finding would also need to be adjudicated through the AE process.
- As noted above, opioid withdrawal effects will be monitored, and a score above 11 on the SOWS will require safety review.
- If physical injury or emotional disruption AEs accumulate (more than 4 minor; easily recovered within one day – or 2 major; requiring more than ASAP intervention to stabilize) then a safety review will be in order.

Such findings are presented to the study statistician or to the Independent Monitoring Committee (IMC) statistician to review the events by group to determine whether there are statistical as well as clinical concerns. The statistician reports his findings to a closed session of the IMC or to the Safety Officer and/or NCCIH. The findings are used to determine what steps will be taken.

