7.5 Followup for Adverse Events

If an adverse event does not require disenrollment and referral to VA physical or mental health services, then the research team will offer adjunctive services for attrition prevention as outlined in the STRONG STAR ASAP SOP (**Appendix O**). Adjunct services and attrition prevention (ASAP) involves the structured provision of extra adjunctive psychotherapy or medical consultation services designed to mitigate risk of adverse events and maintain participants on protocol (within the limits of good ethics and clinical practice). ASAP sessions can be prompted by the participant, an IE, or an interventionist. These sessions are defined in the SOP as “any out of protocol contact (in person or by telephone) lasting longer than 20 minutes. Each participant is allowed three ASAP sessions during protocol intervention. If more intervention is needed, or the PI believes that a higher level of intervention is needed, then the participant will be dropped from protocol treatment and referred for appropriate intervention in the VA. For participants remaining on protocol with ASAP or referral services, progress will be briefed to the PI daily to monitor progress. When the participant and provider report resolution or stability of symptoms, the participant will be re-assessed with the index measure (e.g., PHQ-9 for depression, NRS for pain) and the results will be discussed with the PI (using only the unique identifier for the participant to maintain blinding) for a final determination of resolution and continuation on protocol.

Please note that STRONG STAR maintains a separate SOP for the monitoring, management, and intervention of suicide risk in study participants (as detailed in **Appendix P**). As detailed in the Suicide Risk SOP, all study staff are thoroughly trained in suicide risk assessment, with formal assessments overseen by a licensed psychologist. This SOP describes specific algorithms for risk level determination and pathways for intervention, follow-up, and implications for research involvement.

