8. INTERVENTION DISCONTINUATION

There are few reasons for discontinuing any participant from this study. However, under certain circumstances, it may be necessary to buttress study-related treatment to stabilize temporary conditions needing immediate intervention. The STRONG STAR Research Consortium has established an Adjunctive Services and Attrition Prevention (ASAP) policy (see **Appendix O**) describing a preliminary step for intervention in which a distressed participant will be allowed three out-of-protocol intervention sessions (with their individual or group psychotherapist) of 20 minutes or less to stabilize their condition. Should a pre-determined recovery criterion be met (it is impossible to predict all potential emergencies and goals are determined by committee as described in the ASAP SOP), then the participant will remain enrolled in the study. If recovery is not achieved, then the research team (led by the PI) will

decide on whether the participant should be retained. Those requiring a referral for services outside of the study (i.e., if ASAP is not sufficient for symptom management) will be referred to the appropriate services based on the STRONG STAR Suicide Risk SOP (**Appendix P**), through the VA Hospital (i.e., STVHCS), or using the San Antonio area referrals as described on the STRONG STAR Referral Form (**Appendix R1**). All participants referred for services outside of the study protocol will be tracked using the STRONG STAR Referral Form (**Appendix R2**). If a participant needs to be screened for safety when he/she is outside of the immediate San Antonio area, a distance assessment will be completed as described in **Appendix R3**. The following are examples of conditions/circumstances subject to the ASAP process (all of which would qualify as AEs and be tracked/documented accordingly):

1. *Presence of Suicidal Ideation*: If suicidality is identified during the course of study participation, it is vital that this be addressed and stabilized as quickly as possible. Suicide risk will be monitored, classified, and acted-upon based on the STRONG STAR Suicide Risk SOP.
2. *Physical Injury during PT*: If a participant sustains an injury during PT, [name] will collaborate with [name] or [name] to determine if brief ASAP intervention will help restore function and allow continuation of the study protocol.

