3. *Exacerbation of PTSD or Depression Symptoms*: In any study involving the treatment PTSD, there is a chance that emotional distress may temporarily worsen. If this happens, adjunctive treatment will be provided using the ASAP protocol.
4. *Opioid Withdrawal Symptoms*: During the course of this study, some participants may choose to stop taking opioid medications (though this is not mandatory), which is increasingly likely in light of recent federal changes to VA prescription practices and the VA's Opioid Safety Initiative. Those who discontinue persistent opioid use may report adverse symptoms of opioid withdrawal that will be monitored at all individual, group, and assessment appointments. Should these symptoms be identified, [name] and/or [name] will be notified. They will meet with the PI to discuss if these symptoms can be reasonably addressed under the ASAP protocol.

Participants will continue to be followed with their permission if study intervention is discontinued. There will be no modifications to the schedule and duration of continued followup if the participant is referred to the VA system for treatment and stabilization (though we will ask permission for frequent checks with the participant on their status to ensure that they are doing well and recovering). They will still be asked to complete all measures at all remaining follow-up intervals.

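### The Section 9.4 accumulation trigger is not ordered by severity: an injury or distress AE that outlasts one day but needs no more than ASAP counts toward neither threshold

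*Combined protocol and SAP*

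**What the plan says.** Section 9.4 plans no interim analysis. It lists circumstances that "would require suspension of study activity and review of safety by an ad hoc safety review committee". Two are single-measure triggers: a 20-point rise on the PCL-5, and a score above 11 on the SOWS. The third is a count of physical-injury or emotional-disruption AEs: "more than 4 minor; easily recovered within one day – or 2 major; requiring more than ASAP intervention to stabilize". Findings under these triggers go to a statistician for review by group.

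ASAP is the consortium's adjunctive-services step. Section 7.5 says "Each participant is allowed three ASAP sessions during protocol intervention"; a participant who needs more leaves protocol treatment and is referred to the VA. Section 8 lists the conditions that enter the ASAP process, "all of which would qualify as AEs and be tracked/documented accordingly". For injury during physical therapy (PT), the staff confer "to determine if brief ASAP intervention will help restore function and allow continuation of the study protocol". For worsening PTSD or depression, "adjunctive treatment will be provided using the ASAP protocol".

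No other section of the document defines minor or major for this count, and no middle grade is given.

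**The concern.** The two grades use different scales. Minor has a time limit; major has a management threshold. They would cover every event only if nothing lasting more than a day could settle without care beyond ASAP. The protocol expects otherwise. Section 8 sends PT injuries and worsening distress to ASAP with the aim of keeping the participant on protocol. Section 7.5 allows up to three sessions before re-assessment. Section 5.1 warns that exposure therapy may raise PTSD symptoms during the first week of treatment.

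At stake is the only count in the document that leads from accumulating AEs to a by-group look. The PI rates severity (Section 7.4) but is blind to condition (Section 3), and the weekly meetings discuss participants by identifier to protect that blind (Section 7.3). Case-by-case discussion is therefore not designed to show injuries clustering in the FORT-A arm.

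**Working it through.** The plan gives no figure to reproduce here, so the check applies the rule as written.

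**Classification.** Inputs are the two definitions in Section 9.4.

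| Duration | No help needed | Settled within ASAP | More than ASAP |
|---|---|---|---|
| One day or less | minor | minor | major |
| 2, 7 or 14 days | neither | neither | major |

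**Trigger.** Let a = one-day AEs, b = longer AEs needing no more than ASAP, and c = AEs needing more than ASAP.

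- As written: review if a ≥ 5 or c ≥ 2.
- With b counted as minor: review if a + b ≥ 5 or c ≥ 2.

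| (a, b, c) | As written | b counted as minor |
|---|---|---|
| (5, 0, 0) | review | review |
| (4, 1, 0) | none | review |
| (0, 5, 0) | none | review |
| (4, 1, 1) | none | review |
| (4, 20, 1) | none | review |
| (0, 0, 2) | review | review |

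Moving from (5, 0, 0) to (4, 1, 0) makes one event longer and removes the review, so the rule is not ordered by severity. If the major limb is read as more than 2 (c ≥ 3), the gap remains: (4, 20, 2) gives no review as written and a review when b counts.

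**Illustration under assumed rates.** The documents give no AE rates, so every rate here is an assumption. Take N = 130 and Poisson counts. The chance that the minor count reaches 5 is P(Poisson(m) ≥ 5), with m = 130 × (one-day rate) as written and m = 130 × (one-day rate + longer rate) after the change.

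| One-day rate | As written | Longer rate 1% | 2% | 3% | 5% |
|---|---|---|---|---|---|
| 1% | m = 1.3: 0.01 | m = 2.6: 0.12 | m = 3.9: 0.35 | m = 5.2: 0.59 | m = 7.8: 0.89 |
| 3% | m = 3.9: 0.35 | m = 5.2: 0.59 | m = 6.5: 0.78 | m = 7.8: 0.89 | m = 10.4: 0.98 |

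These figures describe the minor count only. They leave out the major count and the PCL-5 and SOWS triggers. If, as a further assumption, 1% of the 130 participants met a PCL-5 or SOWS trigger, the chance of at least one review from that source alone would be 1 − exp(−1.3) = 0.73.

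**The case against.** The strongest reply is that the parenthesis in Section 9.4 is shorthand, that minor simply means not major, and that the PI grades each AE under an adjudication SOP in any case. On that reading nothing is lost. The monitoring plan and SOPs are not reproduced and may contain the missing grade. Both points stand as limits on the practical effect. They do not rescue the wording: the looser reading works only by setting aside the one-day limit that the rule states.

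Other safeguards also narrow the gap. Section 5.1 labels musculoskeletal injury from PT as serious, and SAEs go to the IRB within 24-48 hours. An injury needing care beyond ASAP is major at any duration. A 20-point PCL-5 rise triggers review as a single event. Pain of 8-10/10 after PT prompts an individual safety check. What remains is mainly longer injuries below the SAE definition and distress of the kind measured by the PHQ-9; none of these safeguards sets a count for them.

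A further objection is that counting longer events would draw in expected effects, such as muscle soreness and early exposure-related distress, both labelled not serious in Section 5.1. That is a real cost. It does not justify the present rule, because milder one-day events of the same kind already count.

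A reader might infer four stronger points that the documents do not support:

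- That longer AEs go unmonitored. They are logged, discussed weekly and reported to the IRB.
- That the chance of a safety review would rise from 0.01 to 0.89. Those values rest on assumed rates and cover one limb of one trigger.
- That the sample log in Section 5.4 shows such an event. It gives no recovery date.
- That the conflict over ASAP session length ("any out of protocol contact (in person or by telephone) lasting longer than 20 minutes" in Section 7.5, "of 20 minutes or less to stabilize their condition" in Section 8) carries the point. Both sections agree on three sessions, and the gap exists under either length.

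**Conclusion.** The concern holds as a defect in the wording of one safety rule. Followed literally, the accumulation trigger ignores any number of injury or distress AEs that last more than a day and settle alone or within ASAP, while five milder one-day events require review. This follows from the text and needs no assumed rate. Because ASAP sessions apply during protocol intervention, the events that clearly fall through are those in the three-week phase settled within ASAP, plus self-resolving events at any time.

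How often this would matter cannot be stated, since the documents give no event rates. Sample size, power and the efficacy analysis are unaffected. The change is worth making, with medium confidence: the defect is clear on the page, but the looser reading or the SOPs and monitoring plan may already close it in practice.

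**What to change.** In Section 9.4, replace the one-day limit so that minor means any physical-injury or emotional-disruption AE that can be stabilised without going beyond ASAP, whatever its duration. Keep major as written. Check the wording against the Data Safety Monitoring Plan and the AE adjudication SOP before it is adopted.

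The drafting cost is one sentence. The operating cost is more safety reviews and, since Section 9.4 ties its triggers to suspension of study activity, possibly more suspensions. Soreness after PT and early exposure-related distress could contribute if they are recorded as such AEs. The monitoring body can limit this by raising the minor count or by excluding named expected effects explicitly, rather than through a duration limit.

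Two side clarifications fit the same amendment. First, reconcile the ASAP session length between Sections 7.5 and 8. Second, state whether AEs defined by PHQ-9 thresholds count as emotional disruption. The second affects volume: a PHQ-9 score of 10 or more is one route to eligibility, and under Section 7.3 a rise above 15, or any increase on item 9, is an AE. Excluding PHQ-9-threshold AEs from the count is another way to limit the number of reviews.
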